9.7.2 Secondary analysis

Not applicable.

9.7.3 Early analysis

No early analysis is planned for this study.

9.7.4 Handling of missing data

The web questionnaire will be programmed in such a way that participants cannot skip questions. We thus do not expect missing values in submitted web questionnaires, and neither replacement nor imputation of missing data is expected to be required. Since there is no applicable method unanimously accepted, there will be no replacement or imputation of missing data in submitted paper vaccinee questionnaires.

9.7.5 Analysis of participation rate

9.7.5.1 *HCP survey*

The following different cases will be distinguished:

- HCPs who do not participate (R): HCPs who do not respond or that explicitly indicate their refusal to participate.
- HCPs with partially answered questionnaires (P): HCPs click on the link provided in the invitation email, and who begin answering the questionnaire but never submit it.
- Failed screening (F): HCPs who will not be eligible for the survey (HCPs who will not meet inclusion criteria and/or who will meet any of the exclusion criteria).
- HCPs with completed questionnaire (C): HCPs who complete the entire questionnaire and submit it.
- Contacted HCPs: HCPs who are contacted by phone or who receive a web link to the online survey via email = C+P+R+F.
- HCPs who agree to participate: HCPs willing to participate in the survey (e.g. by clicking on the link provided in the invitation email) = P+C.

The HCPs participation in the survey will be examined as follows:²⁵

• Response rate = $\frac{C}{C+P+R}$

• Refusal rate = $\frac{R}{C+P+R}$

For HCPs, R, P, F, C and response and refusal rates criteria will be presented overall and by region.

9.7.5.2 Vaccinees survey

- Vaccinees with partially answered questionnaires (P):
 - o For web survey: Vaccinees who click on the link provided and who begin answering the questionnaire but never submit it.
 - o For paper survey: Vaccinees who return partially completed paper questionnaires directly to IQVIA in a prepaid envelope.
- Failed screening (F): Vaccinees who will not be eligible for the survey (vaccinees who will not meet inclusion criteria and/or who will meet any of the exclusion criteria).
- Vaccinees with completed questionnaire (C): Vaccinees who complete the entire questionnaire and submit it (for web) or return to IQVIA (for paper).

For vaccinees, only C, P and F criteria will be presented overall and by region.

9.8 QUALITY CONTROL

9.8.1 Data collection, validation, and data quality control

Data will be collected using a web/paper-administered questionnaire to HCPs and vaccinees. The survey will be conducted according to the Standard Operating Procedures (SOPs) of IQVIA Primary Intelligence and IQVIA Real World Evidence Solutions.

Data from the web-based questionnaire will be collected using an electronic data capture (EDC) system developed following a full validation process. Similarly, data from the paper questionnaire will be entered into the EDC and thereafter validated along with the data collected via the web-based questionnaire. A rigorous System Development Life Cycle that complies with IQVIA Primary Intelligence information technology SOPs will be used for validation. The programmed survey will be tested and validated in accordance with IQVIA SOPs, which cover validation for all clinical and risk management-related applications. The internet-based repository will be used to store survey data and other relevant programme information. Questions are programmed to ensure that they are asked in the appropriate sequence. Skip patterns are clearly indicated. Respondents cannot go back to a question once the question has been answered and cannot skip ahead without answering the previous question. Response options presented in a list are randomised to minimise positional bias. Programming will be reviewed by Quality Control and simulated users (User Testing) prior to implementation. Collected data will be entered and stored in a database specific to the survey. The HCP-identifying information will be stored separately from survey data.

Data will be checked in terms of consistency before data analysis:

- Removal of duplicates (if required)
- Data labelling and data formatting
- Range and consistency checks for each variable to identify potential non-admissible values
- Cross-check the consistency of data for related variables (if feasible).

The number of variables with missing values will be indicated. Missing values are excluded from the calculation of percentages. The study database will be locked once validated.

9.8.2 Data quality control at site level

Not applicable.

9.8.3 Safeguards, security, and traceability of contacts

Operators of the call centre specialised in health surveys, will be assigned to the project and trained on the survey methodology prior to fieldwork. The email contacts and phone calls will be traced using the management software. All survey aspects from protocol development to the reporting of the results will be conducted according to the SOPs of IQVIA Real World Evidence Solutions and Primary Intelligence divisions. These SOPs can be referred on site.²⁶

9.8.4 Compliance to privacy regulations

To be compliant with the privacy regulations, the vaccinee questionnaire will be assessed with the IQVIA RAsT tool, which is developed to assess the risk of patient re-identification. The tool and attendant methodology meticulously check whether the project design and questionnaire could lead to patient identification, even before data collection has been initiated. Not only does the tool show the extent of project risk, but it also provides the researcher with the ability to check the variables that trigger the risk and recommends modifications to these variables.

The evaluation steps are depicted below:

[figure not shown]

Figure 1 Overview of Quality Control Process

Abbreviations: PMR-RAsT: Primary market research-risk assessment tool

The IQVIA Quality Management System (QMS) is built upon the quality and regulatory compliance principles established by the standards and guidelines from the International Standards Organisation and International Conference on Harmonisation of Technical Requirements for Registration of Pharmaceuticals for Human Use (ICH). The QMS encompasses all matters that individually or collectively influence the quality and regulatory compliance of the offerings in scope and defines systems, processes, and tools that enable the proposal to meet the appropriate quality standards and Good clinical practice compliance requirements. IQVIA has implemented an effective support network to ensure that the QMS is embedded across all projects.

- 1. At the study level, all aspects of the study from protocol development to the reporting of the results are conducted within the work-frame of IQVIA QMS and in accordance to the appropriate global procedures.
- 2. A Quality Control checklist will be developed and executed for the study, which will include Quality Control on study methodology, SAP, programming, data management and analysis, study results, conclusions, and study report.

- Furthermore, the study Quality Control plan will establish ownership for the execution of the individual Quality Control steps. The principle of the independence of Quality Control applies.
- 4. Individuals responsible for the execution of the specific Quality Control steps must have knowledge, capability, and experience which are adequate for the task.
- 5. The result of the execution of the individual steps of the Quality Control plan will be documented, and include the required correction actions, if any.
- 6. The execution of any required corrective action will be documented.

Also, the Principal Investigator of the study will verify training compliance of IQVIA employees contributing to the study, as per IQVIA procedure. Examples might be to check the following:

- The data are correctly anonymised
- The variables are in the expected format
- The range of each variable is as expected (e.g. no negative ages)

9.9 LIMITATIONS OF THE RESEARCH METHODS

9.9.1 Strengths

1. Questionnaire design and testing

- Both web questionnaires include general questions followed by specific ones. They
 include both open and closed questions. As the participants (HCPs and vaccinees)
 may understand the right answer in subsequent questions, it will not be possible to
 go back in the questionnaire and edit answers in former questions.
- Both questionnaires will be tested for their clarity. It will also be checked whether there are questions which would suggest a specific answer for any reason, for example social desirability.

2. Experience in drug safety and the evaluation of risk minimisation measures

The study will be conducted by an experienced team specialised in the design and conduct of such surveys in this safety area. It follows IQVIA SOPs, as well as the methodological guidelines from ENCePP and EMA GVP.

3. Quality control and compliance

The information contained in the file of each region of UK (which includes Wales, Scotland, Northern Ireland, England) is updated constantly with proactive updates. Quality controls are implemented on a regular basis by our teams.

In addition, IQVIA has developed a unique risk assessment tool, the IQVIA RAsT, to assess the risk of patient re-identification and ensure compliance with privacy regulations (please see Section 9.8.4).

9.9.2 Limitations

1. Bias

Selection bias

a. HCPs survey

The potential for selection bias of HCPs participating in a survey is an inherent limitation to any study based on volunteer participation. For instance, it is possible that HCPs willing to participate in the study will have the highest awareness of risks associated with use of STAMARIL®. In order to quantify any selection bias, the distribution of each stratification criterion of HCPs (region, HCP profession, and other demographic information collected) will be compared between participants and non-participants.

Non-response bias may also be introduced into the study if targeted HCPs have activated filters in their mailbox that block spam and unsolicited emails. If a very strict degree of message filtering is set, they may not even see the invitation to participate in the survey. Having multiple email addresses could also be a critical situation. If the one used is not the primary address or if the HCPs do not check their emails frequently, they will not receive the invitation during the recruitment period. Some HCPs who are sent a letter may not receive it. This is one of the reasons why the HCPs will also be contacted by phone.

b. Vaccinee survey

For the vaccinees' recruitment by HCPs (who participate or do not participate in the HCPs' survey [in case the target vaccinee sample size is not achieved]), who are aware of the UK (STAMARIL®) yellow fever pre-vaccination checklist and provide the STAMARIL® PIL to the vacinees are more likely to participate in recruiting vaccinees for the patient survey.

HCPs will consecutively solicit vaccinees for participating in the survey. The recruitment of vaccinees will occur in the defined study period and until the limit of ten vaccinees per YFVC is reached. Although consecutive recruitment should minimise selection bias, HCP compliance to this approach cannot be verified. The characteristics of the vaccinees who will not fulfil eligibility criteria cannot be captured, so it is not possible to know the extent of the selection bias.

Information bias

Recall bias may lead to an underestimation of the HCP recalling having received aRMMs. To mitigate the risk of recall bias for HCPs, they will be recruited in the survey if they have provided consultation and/or administered yellow fever vaccines in the past 12 months. Also, to mitigate the risk of recall bias for vaccinees or their parents/guardians if vaccinees are younger than 18 years old, they will be immediately provided with material for the web/paper survey after receiving the vaccine/consultation.

Moreover, web surveys may promote social desirability bias, which refers to the tendency of HCP to give socially desirable/expected responses instead of choosing those reflecting their current knowledge or behaviour, e.g. physicians can copy-paste information gathered online instead of giving their own opinions. Social desirability can affect the validity of survey research findings, but the use of prepopulated items in the questionnaire could/tends to reduce this bias. The access to the web questionnaire interface will be strictly limited to the invited participants, with the possibility to participate only once, and a traceability system. Thus, stakeholder bias (multiple answers of people who have a personal interest in survey results and/or who incite peers to fulfil the survey in order to influence the results) or unverified respondents (when it is not possible to verify who responds) are not applicable.

2. Generalisation of the survey results to the overall target population

In such surveys, the generalisation and external validity of the results is restricted to HCPs/vaccinees who can be reached and are willing (and able) to answer a questionnaire online or paper questionnaire (only for vaccinees). These HCPs/vaccinees may not be fully representative of the whole target population.²⁷

Although the raw survey results cannot be generalised to the overall target population, a sample adjustment will be implemented to allow the generalisation of the results. For more transparency and accuracy, both unweighted (i.e. raw data) and weighted results by region will be presented in the report.

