9.2.4.2 Vaccinee selection

Vaccinees will be primarily recruited by the qualified HCPs who will participate in the HCP survey. In the event that the target sample size of vaccinees is not achieved, then the possibility of recruitment by HCPs who have not participated in the HCP survey will be explored.

Each HCP who has agreed to recruit vaccinees will systematically distribute a kit containing a simplified guide for taking the web or paper questionnaire (as needed) to eligible vaccinees (or their parents/guardians if vaccinees are younger than 18 years old). To limit selection bias, an HCP will be requested to consecutively solicit vaccinees for participating in the survey and a maximum of 10 vaccinees per centre will be recruited.

Vaccinee anonymity will be maintained throughout the study. A unique number will be printed on each page of the questionnaire, which will link each questionnaire with the corresponding HCP who will distribute it. However, no log would be kept at the HCP level which would provide linkage between material for the web/paper survey distributed to the vaccinees (or their parents/guardians if vaccinees are younger than 18 years old) and vaccinee identity. When a vaccinee (or their parent/guardian if vaccinee is younger than 18 years old) fills in the survey on the web/paper, the unique number for the vaccinee survey will ensure that no more than 10 vaccinee questionnaires originate from the same YFVC. Vaccinee recruitment will also be competitive.

Selection bias is reduced through 1) consecutive recruitment of vaccinees by each enrolled qualified HCP, 2) the cap on the number of vaccinees who could be recruited per centre, and 3) the recruitment through both participating HCPs and non-participating HCPs (if the target vaccinee sample size is not achieved) in the survey. As there will be no information linking the vaccinees' identities with the recruiting HCP, there would be no incentive for HCPs to recruit their best vaccinees. There will be incentive for the vaccinees. As there will be no information linking the vaccinees' identities with the recruiting HCP, vaccinees will be unlikely to worry about the answer they provide about the use of the checklist by their HCPs.

Vaccinee recruitment by non-participating HCPs in the survey (if needed):

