In case the desired number of completed vaccinee questionnaires is not achieved during the 12-week period, the data collection period may be extended up to 24 weeks.

Table 3 Example of assumptions for calculation of expected sample size for patients during 12 weeks

Assumptions		2020 (4)
A/ Number of vaccines sold as a proxy for number of vaccinees for 12 weeks (from March to May) (1)	45,984	11,396
B/ Number of active YFVCs	2,989	2,418
C/ Number of HCPs involved in vaccinations	5,668	3,905
D/ Number of vaccinees per center per week ((A/B/12) (2)	1.28	0.39
E/ Number of HCPs who participate in the survey (10% participation rate based on IQVIA experience (3))	567	391
F/ Number of HCPs who agree to distribute material among vaccinees (assumption 10% based on IQVIA		
experience ⁽³⁾)	57	39
Vaccinees response:		
Number of vaccinees who actually receive the survey invitation during 12 weeks fieldwork (F*D*12)	872	184
20% response rate from vaccinees	174	37
10% response rate from vaccinees	87	18

¹⁾ The real number of vaccinees is smaller due to waste and stock.

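### Leaflet receipt is measured through recruiters whom the protocol expects to favour the leaflet; weighting by region cannot correct this, and a partial check with planned data is not specified

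*Protocol*

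**What the plan says.** **Who recruits.** Section 9.2.4.2: "Vaccinees will be primarily recruited by the qualified HCPs who will participate in the HCP survey". HCPs outside the HCP survey are a fallback if the vaccinee target is missed, and they answer only a few screening questions. Table 3 (Section 9.5.2) assumes that 10% of HCPs take the survey and that 10% of those agree to distribute the vaccinee material.

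**The conceded bias.** Section 9.9.2 says that HCPs who are aware of the checklist and provide the PIL "are more likely to participate in recruiting vaccinees for the patient survey". The safeguards in Section 9.2.4.2 are consecutive solicitation, a cap of 10 vaccinees per centre, and the fallback recruiters.

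**What is compared and adjusted.** For the HCP survey, Section 9.9.2 plans that "the distribution of each stratification criterion of HCPs (region, HCP profession, and other demographic information collected) will be compared between participants and non-participants". No similar comparison is planned between HCPs who recruit vaccinees and those who do not. Sections 9.5.3 and 9.7 weight vaccinees by region only, using sales data. Section 9.7.1 describes vaccinees by age range, region, gender and education. Section 9.9.2 then says that the sample adjustment allows the results to be generalised.

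**What could be used.** Q15 of the HCP questionnaire (Annex 6.1) records how often the HCP delivers the PIL. Each vaccinee questionnaire carries a unique number, "which will link each questionnaire with the corresponding HCP who will distribute it". Section 10.3.9 pays an HCP when at least one vaccinee whom he or she recruited completes the survey, so recruiter status has to be known.

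**The concern.** Whether a vaccinee receives the leaflet depends first on whether the HCP hands it out. If HCPs who hand it out are also the ones who volunteer to recruit, the sample is selected on the main determinant of the only vaccinee endpoint, and the error is upward. The first two safeguards govern which vaccinees an HCP approaches and how many come from one centre. They do not govern which HCPs volunteer. The third is conditional, and Section 9.9.2 names the same tendency for fallback recruiters.

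Weighting by region balances England, Wales, Northern Ireland and Scotland. Within a region it leaves the mix of distributing and non-distributing HCPs as recruitment produced it. The Wilson interval does not reflect this error either. At stake is a success verdict against 80% that could owe something to who recruited, in a report that describes the weighted figure as generalisable.

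**Working it through.** **1. Recruiting share, from Table 3.** Inputs for 2019 and 2020: doses sold over 12 weeks 45,984 and 11,396 (row A); centres 2,989 and 2,418 (row B); HCPs 5,668 and 3,905 (row C).

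- Participating HCPs: E = 0.10 × C = 566.8 and 390.5 (printed 567 and 391).
- Recruiting HCPs: F = 0.10 × E = 56.7 and 39.05 (printed 57 and 39).
- Vaccinees per centre per week: D = A / B / 12 = 1.28 and 0.39.
- Invited: F × D × 12 = 872 and 184. Completed at 20% response: 174 and 37.

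Table 3 reproduces. The recruiting share is F / C = 0.10 × 0.10 = 1.0% in both years. This is a planning assumption, not an observed rate.

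**2. Possible size of the overstatement.** The documents give no figure for it. Let d be the share of HCPs who distribute the PIL frequently or always. Assume receipt of 95% when the HCP distributes and 30% when not:

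receipt = 0.95 × d + 0.30 × (1 − d)

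Assume further that 95% of recruiters distribute. Observed receipt is then 0.95 × 0.95 + 0.05 × 0.30 = 0.9175, or 91.8%.

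| Share of all HCP respondents distributing | Receipt across all respondents | Overstatement | 80% crossed? |
|---|---|---|---|
| 90.7% | 0.907 × 0.95 + 0.093 × 0.30 = 0.8896 (89.0%) | 2.8 points | No |
| 75% (assumption) | 0.75 × 0.95 + 0.25 × 0.30 = 0.7875 (78.8%) | 13.0 points | Yes |

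The 90.7% is the share of centres that routinely supplied the leaflet, cited in Section 9.5.1 from the 2020 Annual Return. It is a centre-level figure, used here as a stand-in for HCPs. The 80% line is crossed only if d falls below (0.80 − 0.30) / 0.65 = 76.9%.

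For scale, the 95% margin with 150 vaccinees at 80% is 1.96 × √(0.8 × 0.2 / 150) = 6.4 points. The overstatement runs from under half of that margin to about twice it.

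**3. Can receipt be standardised by Q15?** If 95% of recruiters distribute, 5% of 39 to 57 recruiters is about 2 to 3 non-distributors. At 37 to 174 completed questionnaires they would account for about 2 to 9 vaccinees. That stratum would carry 9.3% of the weight at d = 90.7% and 25% at d = 75%. Section 5 reports only 9 completed vaccinee questionnaires by 24 May 2023, so the stratum could be empty.

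**The case against.** The strongest reply is that the protocol already discloses this bias and its direction, offers safeguards, and restricts external validity to people who can be reached and are willing to answer. It leaves further analysis detail to a SAP, which is not at hand and might add these tables. That stands in part: the fault is not concealment, and nobody can say that the tables will never be produced. But the protocol itself fixes weighting by region and attaches to it a generalisation claim that it cannot carry.

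Several stronger readings are tempting, and the documents do not support them:

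- **A 13-point overstatement that turns failure into success.** This needs a distribution rate near 75%, which appears nowhere in the documents. The one figure they do give, 90.7%, leads to about 3 points and no crossing.
- **Recruiters prompted by having just answered a leaflet question.** Q15 is in the HCP survey, but no interval between that survey and recruitment is stated, and fallback recruiters never answer Q15.
- **The protocol declares HCP self-selection unknowable.** Section 9.9.2 does say that the extent of selection bias cannot be known, but the reason it gives is that characteristics of ineligible vaccinees are not captured.
- **The bias can be fully measured and removed.** Q15 is self-reported, and survey respondents are themselves assumed to be a 10% volunteer sample. Stratifying by Q15 cannot correct a change in behaviour after it was answered.
- **The linked data are ready to use.** The stated use of the questionnaire number is to enforce the cap of 10 per centre. HCP-identifying information is stored apart from survey data (Section 9.8.1) and the HCP log is anonymous (Section 9.6.4). The join is plausible but not confirmed.

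**Conclusion.** The point holds in a limited form. The protocol concedes an upward selection on leaflet practice, plans only region weights for the vaccinee survey, and says that the adjustment supports generalisation. Region weights cannot do that for this kind of selection. A partial check is within reach through Q15, recruiter status and, if it can be joined, the questionnaire-to-HCP number.

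The size is unknown. On the assumptions in the working (receipt of 95% or 30% by the HCP's practice, 95% of recruiters distributing), the overstatement is about 3 points if 90.7% of all respondents distribute and about 13 points if 75% do. Only the second crosses 80%. The case for the check is that the answer depends on a rate the survey will itself record. A reader should not infer that the receipt result will be wrong, or that a false success is likely.

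**What to change.** In Section 9.7.1:

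1. Tabulate Q15 for participating HCPs who recruited at least one vaccinee (or agreed to recruit) against those who did not. This needs no link to vaccinee questionnaires.
2. Report receipt by the recruiting HCP's Q15 answer and by recruiter type (took part in the HCP survey or not). First confirm that the HCP code on the vaccinee questionnaire can be joined to the HCP survey data. Fallback recruiters will have no Q15 answer and form their own row.
3. Standardise receipt to the Q15 distribution of all HCP respondents only as an exploratory estimate, and only if the non-distributing stratum holds enough vaccinees. Set that minimum in advance.

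In Section 9.9.2, limit the generalisation statement to correction of regional imbalance.

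The cost is one or two extra tables with small cells, with no new questionnaire item. The change does not measure prompting by the survey or self-selection into the HCP survey, and the report should say so.
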